Inpatient #2	12	6		10(4) or 10(5) CFU
Inpatient #3	12	6		10(5) or 10(6) CFU
Outpatient	16	8	100	To be determined
Totals	52	26	100	

1. Inpatient trial #1:

The first inpatient trial will admit 18 healthy children age 12-35 months of age with a caretaker, to the ICDDR,B clinical treatment and research facility in Matlab, Bangladesh. Baseline stool and serum specimens will be collected for stool culture and

characterization, and fecal and serum immunoglobulin studies. Children will be randomized to 3 dose groups: 6 will receive a single oral dose of 10^3 CFU SC602 with bicarbonate buffer; 6 will receive 10^4 CFU with buffer; and 6 will receive a placebo (sterile water) and buffer. Close daily monitoring of symptoms and physical examination will be conducted. All stools will be collected for culture and characterization. On day 6, all children will be given antimicrobial therapy prior to discharge. Health workers will collect stool and serum specimens for immunoglobulin assay during home visits on days 14 and 28 following vaccination. Secretory IgA specific for *S. flexneri* 2a LPS will be assayed in stool samples. Anti-*S. flexneri* 2a LPS IgA and IgG will be assayed in serum samples.

Inpatient trials data/specimen collection

Study Day	0	1	2	3	4	5	6	14	28
Vaccinate	X								
Symptoms	X	X	X	X	X	X	X		
Stool cx	X	X	X	X	X	X	X		
Stool/Blood for Ig	X							X	X

2. Inpatient Trial #2

Approximately 2 weeks after the 1st trial is begun, the 2nd inpatient trial will again admit 18 children with their caretaker to the ward. The chosen dose(s) will be administered to 12 children (6 each if 2 doses), and placebo to 6. Children will be followed similarly to trial 1. Stool specimens for culture, and stool and serum specimens for Ig studies will be collected according to the same schedule as in the 1st trial.

Interpretation of optimal dose to be administered in the 2nd inpatient trial will be based on analysis of rates of fecal shedding of SC602, and on rates and severity of symptoms demonstrated during follow up in this 1st trial. The possible doses administered in the 2nd trial will be 10^3 , 10^4 or 10^5 CFU.

Inpatient Trial No. 2 Dose Selection Guidelines:

% Shedding Trial 1	Symptoms Trial 1	Dose 1 (CFU)	Dose 2 (CFU)
<34%	Minimal	10^5	-
<34%	Mild	10^4	10^5
<34%	Mod (few subjects)	10^4	-
<34%	Mod (many subjects)	Stop study	-
35-67%	Minimal - mild	10^4	10^5
35-67%	Mod (few)	10^4	-
35-67%	Mod (many) or Severe (any)	Stop study	-
>68%	Minimal-mild	10^4	10^5

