>68%	Mod (few)	10^3	10^4
>68%	Mod (many) or Severe (any)	Stop study	-

3. Inpatient Trial #3:

If considered to be necessary based on the absence of significant fecal shedding/symptoms in 10^5 CFU recipients, then a 3rd inpatient trial of 10^6 CFU will commence. The design will be identical to the earlier trials, though 10^5 and/or 10^6 CFU will be given to 12 subjects, and placebo to 6. Baseline studies and follow up procedures will be identical. The optimal dose to be administered in the outpatient trial will be determined from the combined data from the inpatient trials.

Inpatient trial No. 3 dose selection guidelines:

% Shedding Trial 2	Symptoms Trial 2	Dose 1	Dose 2
<34%	Minimal	10(6)	-
<34%	Mild	10(5)	10(6)
<34%	Moderate (few)	10(5)	-
34-67%	Minimal-mild	10(5)	10(6)
34-67%	Mod (few)	10(5)	
34-67%	Mod (many), or Severe (any)	Proceed to OP trial with 10(4)	
>68%	Minimal or mild	Proceed to OP trial with 10(5)	

4. Outpatient Trial:

The outpatient trial will enroll 24 children from neighborhoods proximal to the clinical facility, vaccinating them approximately 3 weeks after beginning the 3rd inpatient trial. Additionally, household contacts of these children will be recruited and followed for intestinal symptoms and fecal shedding of SC602. Baseline stool and serum specimens will be collected from vaccine recipients, and processed as before.

Children will be randomized into 2 groups; 16 will receive the single best dose of vaccine identified in the inpatient trials (with buffer), and 8 will receive placebo with buffer. Every day for the first 5 days following vaccination, a study physician will visit the children at home, record symptoms and signs of illness, and perform directed physical examination. Symptoms in household contacts will be recorded as well. A health worker will collect stool samples from vaccinees on days 2, 4, 6, 8 and 10 for culture and characterization. If persistently culture-positive for *Shigella flexneri* on day 10, stools will continue to be collected each 3 days until 2 consecutive stools are culture-negative or until day 28, at which time antimicrobial therapy will be administered to truncate intestinal carriage. Household contacts will have stool collected on days 6 and 10 for culture, and will be asked about intestinal symptoms since the last visit. Stool and serum specimens for immunoglobulin assays will be collected on days 14 and 28 from vaccine/placebo recipients.

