Minor modifications necessitated during the course of the trial, will be made on site as needed, and documented for subsequent review by the chairman of the research review committees at the respective institutions within a reasonable time period. Important methodologic changes that are emergent in nature will be made on site, but the research review committees will be notified within 72 h by oral communication, with written communication following as soon as is reasonably possible thereafter (no later than 2 weeks). Important but non-emergent changes to the protocol will be detailed in writing to the research review committee chairman at least 1 week in advance of the change, with oral communication necessary concomitantly. Incorporation of non-emergent changes will be dependent upon preliminary approval of the changes by the research review committee chairman. If it is felt by the chairman that full committee review is indicated, the trial will be placed on hold until such approval can be granted by the committee, or until 30 days have passed. After 30 days, approval to proceed will be assumed.

Ethical Assurance for Protection of Human Rights

SAFETY MONITORING COMMITTEE

The administration of subsequent doses following the initial inpatient trial will be contingent upon the safety record of the doses, in combination with fecal shedding data. Prior to proceeding with the outpatient trial, an assessment of safety will be made by an independent Safety Monitoring Committee comprised of senior professionals from within and outside ICDDR,B who are in no way involved in the trial.

Causal relationship of vaccine to symptoms will be determined individually, however a causal relationship will generally be implied in vaccinees if temporally associated during the period of observation, regardless of whether or not SC602 is culturable from the stool. In household contacts, the presence of SC602 cultured from the stool will be necessary to establish causality with the above symptoms.

SIGNIFICANT HEALTH EVENTS

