Nalidixic acid is generally well tolerated, but nausea, vomiting and abdominal pain may occur. Allergic reactions such as pruritus, urticaria, various rashes, photosensitivity, eosinophilia and fever occasionally occur and cholestasis, thrombocytopenia, leukopenia and haemolytic anemia rarely occur (Goodman and Gilman, 1996). Co-trimoxazole (trimethoprim-sulfamethoxazole) and ampicillin/amoxicillin are also well-tolerated; the most frequent adverse reactions associated with their use include diarrhea, nausea and abdominal pain. Headache and dizziness occur occasionally, as do hypersensitivity reactions.

There is also the risk of pain, hematoma, or infection at the site of venopuncture.

Recipients may benefit from increased surveillance for diarrheal disease. Diarrhea is highly prevalent in Matlab, and study participants may very well become infected with other wild-type diarrheal pathogens during the course of this study. Diarrhea is eminently treatable in most cases when identified early in the course of disease, however much morbidity and mortality still occur in part due to failure to be promptly evaluated and treated. Monitoring as planned in this study is likely to recognize diarrhea earlier than may otherwise be the case, and thus allow initiation of prompt and appropriate therapy.

MEASURES TAKEN TO MINIMIZE RISK

As mentioned previously, a Safety Monitoring Committee will review the inpatient safety data prior to proceeding with the outpatient trial. In addition, a study monitor will review data after each trial and must concur with study physicians that the planned dose is safe prior to continuing.

All vaccinees will be monitored closely by study physicians for at least 5 days after vaccination. Adverse events reflective of gastrointestinal infection will be promptly addressed according to standard management criteria delineated by WHO guidelines. Non-gastrointestinal illness will be managed according to the standard of medical care provided in Bangladesh. The ICDDR,B treatment center already provides routine medical care for residents of Matlab, and will continue to do so for volunteers in this trial. Adverse events will be reported promptly as per previous discussion of significant health events.

Should an outbreak of symptomatic diarrhea occur in the *baris* of vaccinees, with SC602 isolated from those subjects, the study will be discontinued and all symptomatic subjects will be offered treatment with antimicrobial agents.

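### The Trial 3 dose table presumes Trial 2 gave 10^5; on three routes it did not, and its two outpatient cells then name a dose untried in this age group or one just poorly tolerated

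*Combined protocol and SAP*

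**What the plan says.** Inpatient Trial 1 gives 10^3 to six children, 10^4 to six and placebo to six. The table headed Inpatient Trial No. 2 Dose Selection Guidelines then has ten rows. Three stop the study. Four, all after minimal or mild symptoms, include 10^5. The other three follow a few moderate reactions (the first is labelled "Mod (few subjects") and give 10^4 only, 10^4 only, or 10^3 and 10^4.

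The table headed Inpatient trial No. 3 dose selection guidelines has seven rows, indexed by Trial 2 shedding and symptoms. Two skip Trial 3 and name an outpatient dose:

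- shedding above 68%, minimal or mild symptoms: "Proceed to OP trial with 10(5";
- shedding 34-67%, many moderate or any severe reactions: "Proceed to OP trial with 10(4".

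Other text bears on the choice. The Trial 3 section makes a 10^6 trial depend on a judgement "based on the absence of significant fecal shedding/symptoms in 10^5 CFU recipients", and adds: "The optimal dose to be administered in the outpatient trial will be determined from the combined data from the inpatient trials". Under 4. Outpatient Trial, "16 will receive the single best dose of vaccine identified in the inpatient trials (with buffer". The Safety Monitoring Committee section makes later doses "contingent upon the safety record of the doses, in combination with fecal shedding data". Under Measures Taken to Minimize Risk, the study monitor "must concur with study physicians that the planned dose is safe prior to continuing".

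**The concern.** The Trial 3 table takes no account of which doses Trial 2 used. Where Trial 2 included 10^5, the first cell carries forward a dose already observed on the ward, and the second steps down from it. Where Trial 1 produced a few moderate reactions, Trial 2 was held at 10^4 or below, and both cells lose their logic. The first becomes a tenfold escalation made for the first time in children at home. The second is no longer a step down from Trial 2's top dose, although essentially the same shedding and symptom result after Trial 1 stops the study.

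The setting raises the stakes. Inpatients stay on the ward and all receive antibiotic on day 6. Outpatients are seen at home by a physician for five days and then by health workers every other day to day 10, and every three days after that only if still culture-positive. A vaccinee who sheds without symptoms is treated only at day 28; symptomatic vaccinees and culture-positive contacts are treated earlier (Antibiotics & ORT). The first cell also requires high shedding, which is when spread within the household matters most.

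**Working it through.** **Step 1: trace the routes.** Each of the seven non-stop Trial 2 rows was paired with each Trial 3 row. On the four routes where Trial 2 gives 10^5, the 10^5 cell names a dose already given to inpatients and the 10^4 cell is one step below Trial 2's top dose. On the other three:

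| Trial 1 result | Trial 2 doses | Had 10^4 before outpatients | Had 10^5 |
|---|---|---|---|
| <34%, few moderate | 10^4 | 6 + 12 = 18 | 0 |
| 35-67%, few moderate | 10^4 | 6 + 12 = 18 | 0 |
| >68%, few moderate | 10^3 and 10^4 | 6 + 6 = 12 | 0 |

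All six route-and-cell combinations (3 × 2) fail. The 10^5 cell names a dose no 12-35 month old in this trial has had. The 10^4 cell names the only Trial 2 dose (two routes) or its highest (one route). On that last route some reactions could have come from 10^3.

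**Step 2: how likely are these cells?** The plan gives no figure and does not define few, many or mild in numbers, so these are assumptions: few = 1-3 vaccinees, many = 4 or more of 12, minimal or mild = no moderate case; no severe cases; one moderate rate for all Trial 2 vaccinees; shedding independent of symptoms. With 12 vaccinees, above 68% means at least 9 shedding, and 34-67% means 5-8.

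Moderate rates from the documents: 0/16 (outpatient schoolchildren at 10^4), 2/48 (outpatient schoolchildren, all doses), 1/12 (US inpatients at 10^4, one with mild to moderate symptoms) and 2/22 (schoolchildren on placebo). Shedding at 10^4 was 0/5 in Matlab adult inpatients and 12/12 in US inpatients, so true rates of 30, 50, 70 and 100% are shown.

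Binomial shedding factors, n = 12:

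| True shedding | P(at least 9) | P(5-8) |
|---|---|---|
| 30% | 0.0017 | 0.275 |
| 50% | 0.073 | 0.733 |
| 70% | 0.493 | 0.498 |
| 100% | 1 | 0 |

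**Step 3: the 10^5 cell.** Probability = P(1-3 moderate in Trial 1) × P(0 moderate of 12 in Trial 2) × P(at least 9 shed). The last column assumes only the six 10^4 recipients can react in Trial 1. Products use unrounded factors.

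| Moderate rate | First two factors, 12 at risk | First two factors, 6 at risk |
|---|---|---|
| 0/16 | 0 | 0 |
| 2/48 | 0.399 × 0.600 = 0.239 | 0.225 × 0.600 = 0.135 |
| 1/12 | 0.634 × 0.352 = 0.223 | 0.406 × 0.352 = 0.143 |
| 2/22 | 0.663 × 0.319 = 0.211 | 0.435 × 0.319 = 0.138 |

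Multiplying the non-zero range 0.135-0.239 by the shedding factor gives 0.02-0.04% at 30% shedding, 1.0-1.7% at 50%, 7-12% at 70% and 14-24% at 100%.

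**Step 4: the 10^4 cell.** Probability = P(1-3 moderate in Trial 1) × P(at least 4 of 12 moderate in Trial 2) × P(5-8 shed).

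- At 2/48, 1/12 and 2/22 the first two factors give 0.0005, 0.0088 and 0.0123. The largest result at the shedding rates shown is 0.0123 × 0.733 = 0.009.
- At an assumed moderate rate of 25%: 0.617 × 0.351 = 0.217, giving 0.060, 0.159 and 0.108 at 30, 50 and 70% shedding. With six at risk in Trial 1: 0.784 × 0.351 = 0.276, giving 0.076, 0.202 and 0.137.

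Severe reactions are left out, although any one of them in Trial 2 satisfies this cell's symptom condition.

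**The case against.** The strongest reply is that these are guidelines, to be read with the rest of the protocol. The outpatient dose is to come from the combined inpatient data and be the best dose identified there, and later doses depend on the safety record. On that reading the text already points away from an unobserved 10^5 and from a 10^4 that has just caused trouble. The Trial 3 section speaks of 10^5 recipients, so its table was evidently written for a Trial 2 that gave 10^5; the three routes are then an unaddressed case, not an instruction to give the wrong dose. The study monitor must agree after each trial, and an independent committee assesses safety before the outpatient trial. The 10^5 dose had been given to Matlab adults and to 3 + 16 = 19 schoolchildren without severe symptoms. The probabilities rest on assumed cut-offs. The one schoolchild rate at 10^4, 0/16, makes both cells impossible, and SC602 was not isolated from any vaccinee in the Matlab adult outpatient trials.

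Much of this stands: it lowers the chance of harm and makes the probabilities illustrative. It does not repair the cells. The sentence about 10^5 recipients is a condition for starting a 10^6 trial; it does restrain the table's 10^6 rows, but not the two outpatient cells. The general sentences conflict with those cells without saying what to do instead, so staff would have to set the tabulated entry aside to follow them. Experience in older groups is limited reassurance: the protocol's own section on age range warns that including children over 36 months could understate risk in the younger target group.

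**Conclusion.** The concern holds. On three of the seven non-stop routes out of Trial 1, both cells that name an outpatient dose give a wrong answer when read literally, affecting up to 16 outpatient vaccinees. This is a gap in a written dose rule, not a certain exposure. The chance of meeting the 10^5 cell is zero if moderate reactions do not occur, negligible at 30% shedding, and 7-24% at 70-100% shedding with moderate rates of 2/48 to 2/22. The 10^4 cell is under 1% at those rates and 6-20% only at an assumed 25% moderate rate with 30-70% shedding. These figures depend on the cut-offs and independence assumed above; the route tracing does not. Where Trial 2 did give 10^5, the 10^5 cell is not disputed. The rule should be corrected before Trial 2 begins.

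**What to change.** Make both outpatient cells conditional on 10^5 having been given in Trial 2. For the 10^4 cell, also require that the many-moderate or severe reactions did not occur at 10^4. Add one sentence for every other case: proceed only with a dose already given to, and tolerated by, inpatients in this trial; if 10^5 is still wanted, give it first in inpatient Trial 3; if no tested dose qualifies, stop, as after Trial 1. Nothing else in the two tables needs to change for this point.

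The cost is a condition on two cells and one sentence, amended before Trial 2. The downside is that inpatient Trial 3, with 18 children already counted in the planned 78, may have to run on routes where the present table would skip it.

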1. Oral administration of SC602 to healthy Bangladeshi children from 12 to 35 months of age in dose levels less than or equal to 10^6 CFU will not lead to significant adverse events.
2. The dose that consistently colonizes vaccine recipients and is safe, will also induce evidence of immune stimulation.
3. There may be some secondary spread of vaccine to household contacts of vaccine recipients, but there will be no vaccine-induced occurrence of dysentery/diarrhea.

Specific Aims

1. To evaluate adverse events associated with oral administration of up to 4 dose levels of SC602 [10^3 , 10^4 , 10^5 or 10^6 CFU] relative to placebo in healthy children 12-35 months of age in a community endemic for *Shigella*.
2. To evaluate duration of fecal shedding of SC602 in these children for up to 28 days after vaccination.
3. To evaluate probability of, and symptoms associated with, secondary spread of SC602 to household contacts of vaccinated children as determined by stool culture of these contacts for the vaccine strain.
4. To evaluate humoral immune responses in serum and stool, manifested by changes in immunoglobulins.

Background of the Project

Epidemiology.

The 4 species of the genus *Shigella* are the most common bacterial cause of severe bloody diarrhea (bacillary dysentery) worldwide. In the developing world, *Shigella flexneri* predominates, with *S. flexneri* 2a specifically the predominant serotype. Studies from the Matlab, Bangladesh field research station of the ICDDR,B reveal that in 8-10% of all deaths in 1-4 year old children are due to bloody diarrhea. Stool cultures from subjects with diarrhea (all clinical variants) in this population reveal shigellae in 8-12% of specimens; about 60% of which are *S. flexneri*. In a community-based cohort study of 700 <5 years old children in this area, the attack rate of *Shigella*-

associated diarrhea was 25 episodes per 100 child-years, and 15 episodes per 100 child-years for *S. flexneri* (Baqui et al, 1992). Globally, 65% of *Shigella* cases occur in children <5 years old. In the developing world, overall, 60% of cases are associated with *S. flexneri*, with 32-58% being the *S. flexneri* 2a serotype. *S. sonnei* predominates in the developed world (77% of isolates) (Kotloff et al, unpublished). The incidence of clinical shigellosis peaks at 1-4 year old children and decreases to approximately 25% of peak levels in older children and adults living in endemic areas (Keusch et al, 1991; Slayers et al, 1994).

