buffer, and 4 received buffer alone. This design was repeated for the 5 log and 6 log CFU doses, except that 4 additional subjects were given buffer alone. Symptoms and fecal excretion of SC602 were monitored among vaccinees and their household contacts for up to 56 days. Diarrhea was not reported at any of the vaccine dose levels. Minor symptoms were commonly reported among most study participants, but there was no difference between vaccinees and controls and no dose-relationship. In the 6 log CFU dose group, 1 vaccinee had low grade fever, and 2 reported body aches. No increase in symptoms was seen among household contacts. SC602 was not isolated from any vaccinee, household contact or diarrhea case occurring in the neighborhood. The adult trials suggest minimal vaccine shedding, minimal reactogenicity, no transmission risk, and little immune stimulation in this *Shigella*-exposed population.

Inpatient trial: schoolchildren

Nine subjects age 5-15 years old were randomized 3 each to receive 10^4 , 10^5 or 10^6 CFU. No severe symptoms, fever or diarrhea followed vaccination, though 1-2 loose stools occurred in 4 of 9, and abdominal pain in 2 of 9. All symptoms were mild, except 1 report of moderate abdominal cramps in a 6 log CFU recipient.

Overall, symptoms were not serious and not dose related. One subject passed a few drops of blood of unclear origin on day 5 with normal stool and did not excrete SC602. Stool microscopy revealed <10 WBC's per HPF, hookworms and other worms. Rectal examination was unrevealing. The passage of few drops of blood for a day was considered due to some local lesion, e.g., anal fissure.

Outpatient trials: School children

Four, 5 or 6 logs CFU or placebo were given to a total of 70 children. Vaccinees and household contacts were followed for symptoms and shedding. Once again, no diarrhea, dysentery or severe symptoms were experienced. Loose stools occurred in 15% of vaccinees, but 9% of controls. Abdominal pain was reported in 21% of vaccinees, but 14% of controls. Symptoms were otherwise not more common in vaccinees than in controls, and no dose relationship was apparent. Secondary transmission to household contacts was not demonstrated.

Signs and symptoms in inpatient school children:

Symptoms	4 log (n=3)	5 log (n=3)	6 log (n=3)	Total (n=9)
Diarrhea	0	0	0	0
Loose stool	0	3	1	4
Bloody stool	0	1	0	1
Nausea	1	0	1	2
Vomiting	1	0	0	1
Abdominal pain	1	0	1	2
Fever*	0	0	0	0
Headache	1	0	1	2
Body aches	0	0	0	0
Malaise	1	0	2	3

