Joint pain	0	0	0	0
Gas	2	0	0	2
Anorexia	1	1	2	4
Others	2	0	0	2
Summary of symptoms				
Mild	3	3	1	7
Moderate	0	0	1	1
Severe	0	0	0	0
Any symptom	3	3	2	8

Signs and symptoms in outpatient schoolchildren:

Symptoms (%)	Dose(CFU)			
	4 log (n=16)	5 log (n=16)	6 log (n=16)	Placebo (n=22)
Diarrhea	0	0	0	0
Dysentery	0	0	0	0
Loose stools	1	4	2	2
Abdominal pain	4	3	3	3
Headaches	5	2	3	3
Fever	1	0	0	2
Any mild	8	9	6	9
Any moderate	0	1	1	2
Any severe	0	0	0	0

In summary, the school children trials demonstrated SC602 to be well tolerated, with mild symptoms in about half, and moderate symptoms rarely. Loose stools and mild abdominal cramps may occur somewhat more commonly than in controls, though not remarkably so. Secondary transmission of vaccine was not evident.

The combined trials in adults and school children support further efforts to evaluate the vaccine in small numbers of children in the target population age range of 1-5 years. This study is designed towards that end.

Research Plan

STUDY DESIGN

A randomized, double-blind, placebo-controlled clinical trial is proposed, conducted in 4 phases. The first 3 phases will be inpatient trials directed primarily at determining the safety and optimal dose of SC602 in the target age group of 12-35 months old children. Healthy children will be admitted in ICDDR,B Matlab research facility after screening and taking consent. Children will be followed closely for symptoms, fecal shedding of vaccine, and immune markers. After 5 days of observation, they will be treated with an antimicrobial if shedding *Shigella* to truncate intestinal colonization prior to discharge. The volunteers will be requested to come to Matlab on days 14 and 28 for submission of blood and stool specimens. On the basis of these studies, the optimal dose in this age group will be chosen. The outpatient trial will follow, in 12-35 months old children, and providing only the single dose chosen in the inpatient trials, or placebo. The additional intent of the outpatient trial is to assess risk for secondary transmission from vaccine recipients to household contacts. These trials will administer vaccine or placebo to 78 children, and monitor about 100 household contacts for secondary transmission. These studies will form the basis for consideration of further safety and/or efficacy trials of SC602 in this population.

Number of subjects enrolled in the trials

Trial	Vaccine	Placebo	Household contacts	Dose
Inpatient #1	12	6		10(3) or 10(4) CFU

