Four small trials will be conducted in sequence as part of this protocol. Up to three inpatient trials will be followed by an outpatient trial. The inpatient trials will enroll 18 subjects each, of whom 12 will receive vaccine and 6 placebo. The outpatient trial will enroll 24 subjects, providing vaccine to 16 and placebo to 8. Additionally, as part of assessment for secondary transmission risk, household members will be recruited for participation in a minimal risk aspect of the outpatient trial, collecting only 2 stool samples and symptom responses. No medication or vaccine will be provided to this population, unless symptomatic intestinal disease is apparent and/or the vaccine strain is cultured from their stool. In that case, standard antibiotic treatment will be provided. Assuming 5 household members per vaccinee in the outpatient study, about 100 household members will be enrolled.

As a phase 1 trial in young children, sample size considerations are relatively less important than safety concerns. Our sample size has been determined based on three considerations:

We feel an ethical obligation to perform the trial in as safe a manner as possible. That is why we escalate the dose sequentially in the inpatient studies, providing only the very lowest doses initially, rather than expose all subjects at once. That is also why we expose the fewest number of volunteers possible.

Logistical considerations. How many volunteers are available to participate, and how many can be accommodated and monitored adequately in the facilities at our disposal?

Statistical considerations. With at least 12 volunteers receiving the chosen dose, and

20 placebo, if none of the placebo recipients and a third of the vaccinees experience an adverse event, there will be >80% power to detect this difference with >95% significance level by Fisher Exact Test. Similarly, if none of the placebo recipients sero-convert, and at least one third of the vaccinees at the chosen dose sero-convert, we will be able to detect that difference with >80% power and >95% significance by Fisher Exact Test.

OUTCOME VARIABLES

Clinical

- Adverse events in study subjects.
- Secondary transmission of SC602 to household contacts of vaccinees.
- Adverse events in household contacts of vaccinees.

Laboratory

- Occurrence and duration of fecal shedding of the vaccine strain.
- Immune response as measured by changes in anti-*S. flexneri* 2a LPS secretory IgA in stool, and IgA and IgG in serum.

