A significant health event occurring during the surveillance period of the study will be defined in the two categories denoted below. These events will be immediately (within 24 h) reported to the Chairman of ICDDR,B Ethical Review Committee and the USAMRMC Deputy Chief of Staff for Regulatory Compliance and Quality [contact] (non-duty hours call [contact] and send fax to [contact]). A written report will follow the initial telephone call within 3 working days. Address the written report to the US Army Medical Research and Materiel Command, ATTN: MCMR-RCQ-HR, [name].

Serious adverse experience:

A serious adverse experience is any event that is life-threatening or permanently disabling. An adverse event is any unfavorable and unintended sign, symptom, or disease temporally associated with the use of a medicinal product, whether or not considered related to the medicinal product.

Unexpected adverse experience:

Any adverse event that is not identified in nature, severity or frequency in the current investigator's brochure or general investigational plan.

RISKS AND BENEFITS TO VOLUNTEERS

Signs and symptoms associated with the ingestion of the vaccine may include abdominal cramping, diarrhea with or without blood/mucus, fever, malaise, muscle and/or joint aches, headache, tenesmus, nausea and vomiting. In previous studies at the same dose, these signs and symptoms were generally mild or did not occur. Reactive arthritis due to *Shigella flexneri* has not been demonstrated in Bangladesh and is felt to represent an extremely low risk, nevertheless, should sterile inflammatory arthritis develop in any vaccinee, HLA B27 testing will be performed. Arthritis has never been documented in any SC602 vaccine recipient in either US or Bangladeshi residents. Mild gastrointestinal symptoms may also be experienced with ingestion of the bicarbonate buffer alone. Clinical dysentery (bloody diarrhea with fever) will be considered as a severe adverse event. All other signs/symptoms mentioned will be graded as mild, moderate or severe.

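### The >80% power for adverse events holds only if no placebo child has an event; at the protocol's own placebo rates, power at the stated 12 versus 20 is about 52% or lower

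*Combined protocol and SAP*

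**What the plan says.** Under SAMPLE SIZE, the statistical consideration takes a minimum of 12 vaccinees at the chosen dose and states: "20 placebo, if none of the placebo recipients and a third of the vaccinees experience an adverse event, there will be >80% power". The test is specified as "with >95% significance level by Fisher Exact Test". The sentence does not say which adverse events it means or whether the test is one- or two-sided.

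Under SIGNIFICANT HEALTH EVENTS the definition is broad: "An adverse event is any unfavorable and unintended sign, symptom, or disease temporally associated with the use of a medicinal product", related or not. RISKS AND BENEFITS TO VOLUNTEERS adds that the bicarbonate buffer by itself may produce mild gastrointestinal symptoms. Every placebo child receives buffer.

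The background reports the previous outpatient trials in children aged 5-15 years: "Loose stools occurred in 15% of vaccinees, but 9% of controls" and "Abdominal pain was reported in 21% of vaccinees, but 14% of controls". The accompanying table gives, for 22 placebo children, fever in 2, any mild symptom in 9, any moderate symptom in 2, and no diarrhea, dysentery or severe symptom. In the adult outpatient trials, minor symptoms were common and did not differ between vaccinees and controls.

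**The concern.** Adverse events are the subject of the first hypothesis and the first specific aim, and they are the first listed outcome. The Analysis section compares them between vaccine and placebo. The power sentence is the only quantitative support for that comparison, and it rests on a placebo rate that the protocol's own definition and earlier placebo data contradict for most symptoms.

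The zero matters because the Fisher test at these sizes is very sensitive to the first placebo event. If true power is well below 80%, a non-significant comparison says little about whether the vaccine causes symptoms, yet the stated figure would make it look informative.

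**Working it through.** **Inputs.** Vaccinees 12, placebo 20, rates 1/3 and 0, significance level 0.05, Fisher exact test (SAMPLE SIZE). Placebo rates from the outpatient schoolchildren table:
- fever, loose stools, any moderate symptom: 2/22 = 9% each
- abdominal pain: 3/22 = 14%
- any mild symptom: 9/22 = 41%
- diarrhea, dysentery, severe symptoms: 0/22

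**Formula.** With X events among n1 vaccinees and Y among n0 placebo children, power = Σ P(X = x | n1, p1) · P(Y = y | n0, p0), summed over all tables with two-sided Fisher p ≤ 0.05 and a higher observed rate on vaccine.

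**Step 1: the plan's figure.** With 0/20 on placebo, 2/12 gives p = 0.133 and 3/12 gives p = 0.044. So power = P(X ≥ 3 | 12, 1/3) = 1 − 0.0077 − 0.0462 − 0.1272 = 81.9%. A one-sided test gives the same value. The claim reproduces.

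**Step 2: one placebo event.** 4/12 versus 1/20 gives p = 0.053; 5/12 versus 1/20 gives p = 0.018. One event among 20 placebo children therefore raises the threshold from 3 to 5 of 12. At a 9% placebo rate, the chance of at least one event among 20 is 1 − (20/22)^20 = 85%.

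**Step 3: power at 12 versus 20 with documented placebo rates.** Two scenarios are kept apart, because they answer different questions.

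| Placebo rate | Vaccine rate stays at 1/3 | Vaccine rate = placebo + 33 points |
|---|---|---|
| 0% | 82% | 82% |
| 9% | 31% | 52% (vaccine 42%) |
| 14% | 20% | 47% (vaccine 47%) |
| 41% | <1% (placebo exceeds vaccine) | 34% (vaccine 74%) |

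**Step 4: the sizes that the design yields.** The 20 placebo equals 6 + 6 + 8, that is, two inpatient trials pooled with the outpatient trial; a third inpatient trial makes it 26. Pooled the same way, the chosen dose has at least 6 inpatients + 16 outpatients = 22 vaccinees. Two six-child inpatient groups at that dose give 28. Where the dose-selection tables assign one dose to all 12 vaccinees of a trial, the total can reach 6 + 12 + 16 = 34 or 12 + 12 + 16 = 40. Power at a 9% placebo rate:

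| Vaccine vs placebo | Vaccine rate 1/3 | 33-point excess |
|---|---|---|
| 22 vs 20 | 44% | 69% |
| 28 vs 26 | 52% | 79% |
| 34 vs 26 | 57% | 83% |
| 40 vs 26 | 60% | 85% |

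At 22 versus 20 with 9% on placebo, a vaccine rate of 47% gives 79% power and 48% gives 81%, so 80% power needs a vaccine rate of about 48%.

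**The case against.** The strongest reply is that nothing is miscalculated. The sentence is openly conditional on zero placebo events, and the figure reproduces. The plan also ranks statistics behind ethics and logistics in a phase 1 trial. Dose steps rest on shedding and symptom severity, a study monitor must concur, and an independent committee reviews safety before the outpatient trial. All of this stands. The point concerns a planning assumption, and it does not show that safety oversight depends on this test.

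A second reply is that the sentence may mean serious events only. For diarrhea, dysentery and severe symptoms the earlier placebo data are 0/22, and zero is then a reasonable planning value. That also stands, but the sentence does not say so, and the protocol's definition points the other way.

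A third is that the placebo rates come from children aged 5-15. Some of those symptoms, such as abdominal pain, rely on self-report. The rates are the closest placebo data that the protocol gives, but carrying them over is an assumption. Choosing a one-sided test would not rescue the claim: at 12 versus 20 a 33-point excess over 9%, 14% or 41% has 53%, 50% or 45% power.

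Four stronger readings are tempting and not supported:
- **That the design cannot detect a one-third excess at all.** The 34 versus 26 and 40 versus 26 paths reach 83% and 85% for a 33-point excess over 9%.
- **That half of the placebo schoolchildren had some symptom.** This adds 9 mild and 2 moderate. The outpatient table has no any-symptom row, so 41% is the highest printed rate.
- **That even diarrhea alone would rarely be zero on placebo.** One could divide the cohort's *Shigella* attack rate by the culture share ("Stool cultures from subjects with diarrhea (all clinical variants) in this population reveal shigellae in 8-12% of specimens"), but the protocol does not show that the two figures share a source, and the enrolled children are screened for recent diarrhea. The direct observation is 0/22.
- **That a non-significant result will be taken as proof of safety.** No passage says this. It is a risk of the wording.

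**Conclusion.** The concern holds in limited form. The >80% figure is arithmetically right but applies only to events that do not occur on placebo. For adverse events as the protocol defines them, at the stated 12 versus 20 and the documented placebo rates of 9% to 41%, two-sided power is 31% or less if the vaccine rate stays at one third, and 34% to 52% for a 33-point excess. At the minimum pooled size of 22 versus 20, power at 9% placebo is 44% or 69%.

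This rests on three assumptions: that the power sentence covers events under the general definition, that the schoolchildren's placebo rates carry over to ages 12-35 months, and that the test is two-sided at 0.05. The zero-placebo assumption made for seroconversion in the same paragraph is not examined here.

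**What to change.** In the sample size section:

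1. Name the adverse events that the power sentence covers, and state whether the test is one- or two-sided.
2. Keep the zero-placebo figure only for events with 0/22 in the earlier placebo children: diarrhea, dysentery and severe symptoms.
3. For any, mild or moderate symptoms, restate power at non-zero placebo rates with the sizes that the design yields. For example: with 22 vaccinees and 20 placebo recipients and a 9% placebo rate, 80% power requires a vaccine rate of about 48%. State that the placebo rates come from ages 5-15.
4. In the Analysis section, report differences in these symptoms with exact confidence intervals, as estimation and not as a powered test.

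The cost is wording and a less favourable stated power. No additional children are needed.
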